10.2	AUDITING AND INSPECTING.....	23
11	ETHICAL CONSIDERATIONS	23
11.1	INFORMED CONSENT	23
12	STUDY FINANCES.....	23
12.1	FUNDING SOURCE.....	23
12.2	CONFLICT OF INTEREST.....	24
13	PUBLICATION PLAN	24
14	REFERENCES	25

List of Abbreviations

AE	Adverse Event
BID	twice daily
BMP	basic metabolic panel
CBC	complete blood count
CFR	Code of Federal Regulations
CMV	cytomegalovirus
CRF	Case Report Form
DSMB	Data and Safety Monitoring Board
DSMP	Data and Safety Monitoring Plan
EBV	Epstein-Barr virus
FDA	Food and Drug Administration
GCP	Good Clinical Practice
HIPAA	Health Insurance Portability and Accountability Act of 1996
ICH	International Conference on Harmonization
IDS	Investigational Drug Services
IRB	Institutional Review Board
KTx	kidney transplant
PCR	Polymerase Chain Reaction
PHI	Protected Health Information
SAE	Serious Adverse Event
QD	once daily
QOD	every other day
valA	valAcyclovir
valG	valGanciclovir

Study Summary

Title	Valacyclovir versus Valganciclovir for Post-transplant Cytomegalovirus/Epstein-Barr Virus Prophylaxis: A Randomized Controlled Trial
Short Title	ValA vs ValG for Post-transplant CMV/EBV Prevention
Protocol Number	11.0
Phase	Pilot
Methodology	Randomized Control Trial
Study Duration	36 months
Study Center(s)	Single-Center
Objectives	To compare the effectiveness of valacyclovir (valA) to valganciclovir (valG) in the prevention of EBV and CMV viremia post-kidney transplant.
Number of Subjects	Total of 200
Diagnosis and Main Inclusion Criteria	Adult and pediatric kidney transplant recipients
Study Product, Dose, Route, Regimen	Valacyclovir Dose: 500-1500mg bid Oral
Duration of administration	3-12 months dependent on treatment assignment and donor and recipient viral serostatus in accordance with standard of care.
Reference therapy	Valganciclovir Oral
Statistical Methodology	Incidence of viremia will be compared using a two-sided Fisher exact test and viral load-time curve areas will be compared using a Mann-Whitney test. A p-value of ≤ 0.05 will be considered significant.

1 Introduction

Infections are now a leading cause of death and morbidity in kidney transplant recipients. Herpes viruses such as Epstein-Barr virus (EBV) and cytomegalovirus (CMV) are particularly troublesome.

At the present time, valganciclovir (valG) is the primary prophylactic agent against CMV in kidney transplant (KTx) recipients. Although many centers try to prevent CMV disease by placing all or in some centers, only the high risk patients (defined as CMV antibody negative patients receiving organs from CMV antibody positive donors) on antiviral prophylaxis with valG for three to 12 months post-KTx, there continue to be patients with break-through infections. CMV viremia has been noted in 22% of pediatric post-KTx recipients, and the incidence at the University of Minnesota (UMMC) in all KTx recipients is as high as 17% despite valG prophylaxis. CMV disease post-KTx can manifest as fever, leucopenia, or mild to severe organ involvement. While an effective anti-CMV drug, valG has a number of adverse effects including leucopenia, also a side effect of mycophenolate mofetil (MMF), one of the cornerstones of current anti-rejection regimens. Combined therapy with MMF and valG frequently results in leucopenia associated infection or leucopenia necessitating reduction in MMF doses, increasing the risk of rejection. In addition, valG is prohibitively expensive. Therefore, rather than prophylaxis, many centers adopt a pre-emptive therapeutic approach whereby post-KTx patients are screened for CMV, and at new onset viremia, valG is initiated. This approach has been associated with increased CMV infections and resistant viral strains.

Therefore, there is need for an alternate drug with a more benign side effect profile and equal effectiveness against CMV. Valacyclovir (valA) was shown to reduce the incidence and delay the onset of CMV disease in both CMV seronegative patients ($P<0.001$) and CMV seropositive patients ($P=0.03$) and has fewer severe adverse events. In fact, very high doses of valA (8g/day), for post-KTx CMV prophylaxis were shown to have no severe or treatment-limiting side effects compared to placebo.

Currently, prevention of EBV infection is conducted by close monitoring of patients and immunosuppression reduction at the discovery of EBV viremia. A recent study suggested that valG prophylaxis post-KTx is protective against EBV infection, but it had design flaws and the number of subjects was limited. Therefore to date, the anti-EBV effect of valG is poorly defined. EBV can present post-KTx as infectious mononucleosis syndrome, hepatitis and, most importantly, can initiate potentially fatal lymphoproliferative disorders (PTLD). Between October 2003 and December 2009, EBV viremia occurred in 20% of adults and 50% of pediatric KTx recipients (60/120) at UMMC, and, PTLD occurred in 6% (7/120) of pediatric recipients. Effective anti-EBV prophylaxis could substantially improve KTx outcomes. ValA therapy resulted in a statistically significant reduction in oral EBV shedding, accompanied by a clinical benefit, and valA is currently used for the therapy of severe cases of infectious mononucleosis in the community.

This document is a protocol for a human research study. This study will be conducted according to US and international standards of Good Clinical Practice (FDA Title 21 part

312 or 812 and International Conference on Harmonization guidelines), applicable government regulations and Institutional research policies and procedures.

1.1 *Background*

Therefore as stated above CMV and EBV remain critical posttransplant complications that can significantly and negatively impact patient and kidney transplant survival. In addition to overt CMV and EBV related issues detailed above, subclinical CMV and/or EBV viremia have been associated with deterioration in kidney function in KTx recipients. The significance of this research also includes the potential for substantial cost-savings. At UMMC, even with discounted pricing due to the University status and bulk ordering, a 90 day supply of 450mg doses of valG administered twice daily is approximately \$11,000 compared to \$3250 for 1.5g tablets twice daily of valA. At least 200 patients receive kidney transplants each year at UMMC, making the impact of a successful outcome from this research a saving of at least \$1.55 million per year in addition to the cost-saving of reducing viral infection or rejection related admissions and expenses.

UMMC conducts surveillance biopsies at 3 and 12 months post-KTx on some adult transplant recipients, providing an ideal opportunity to assess kidney tissue for EBV and CMV via molecular and immunological assays. We think it likely that post-KTx, kidneys exposed to an immunosuppressed milieu allowing viral multiplication will increase the likelihood of isolating the virus from infected recipients; a pivotal step in our understanding of the mechanisms of CMV and EBV infection post-KTx.

In summary, valA is less expensive, with fewer adverse effects, and less likelihood of causing leucopenia than valG. If this agent has equivalent efficacy in CMV and any efficacy in EBV prophylaxis, the use of valA will result in significant financial savings, a reduced risk of leucopenia-associated infection, and a lower incidence of rejection by allowing the use of standard MMF doses.

1.2 *Investigational Agent*

Valacyclovir (valacyclovir hydrochloride) is the hydrochloride salt of the *L*-valyl ester of the antiviral drug acyclovir. Caplets are for oral administration. Each caplet contains valacyclovir hydrochloride equivalent to 500 mg or 1 gram valacyclovir and the inactive ingredients carnauba wax, colloidal silicon dioxide, crospovidone, FD&C Blue No. 2 Lake, hypromellose, magnesium stearate, microcrystalline cellulose, polyethylene glycol, polysorbate 80, povidone, and titanium dioxide. The blue, film-coated caplets are printed with edible white ink.

Valacyclovir oral suspension (25 mg/mL or 50 mg/mL) may be prepared extemporaneously from 500 mg VALTREX Caplets for use in pediatric patients for whom a solid dosage form is not appropriate.

The chemical name of valacyclovir hydrochloride is *L*-valine, 2[(2-amion-1,6-dihydro-6-oxo-9*H*-purin-9-yl)methoxy]ethyl ester, monohydrochloride.

Valacyclovir is a nucleoside analogue DNA polymerase inhibitor. Valacyclovir hydrochloride is rapidly converted to acyclovir which has demonstrated antiviral activity against HSV types 1 (HSV-1) and 2 (HSV-2) and VZV both in cell culture and *in vivo*. The inhibitory activity of acyclovir is highly selective due to its affinity for the enzyme thymidine kinase (TK) encoded by HSV and VZV. This viral enzyme converts acyclovir into acyclovir monophosphate, a nucleotide analogue. The monophosphate is further converted into diphosphate by cellular guanylate kinase and into triphosphate by a number of cellular enzymes.

Valganciclovir (valganciclovir hydrochloride) contains valganciclovir hydrochloride (valganciclovir HCl), a hydrochloride salt of the *L*-valyl ester of ganciclovir that exists as a mixture of two diasteromers. Ganciclovir is a synthetic guanine derivative active against CMV.

Tablets are available as 450 mg for oral administration. Each tablet contains 496.3 mg of valganciclovir HCl (corresponding to 450 mg of valganciclovir), and the inactive ingredients microcrystalline cellulose, povidone K-30, crospovidone and stearic acid. The film-coat applied to the tablets contains Opadry Pink.

For pediatric patients, valganciclovir HCl is available in an oral solution that must be prepared by a pharmacist prior to dispensing. Valganciclovir HCl for oral solution (50 mg per mL) is supplied as a white to slightly yellow powder for constitution, forming a colorless to brownish yellow tutti-frutti flavored solution. Available in glass bottles containing approximately 100 mL of solution after constitution.

Valganciclovir is an *L*-valyl ester (prodrug) of ganciclovir that exists as a mixture of two diastereomers. After oral administration, both diastereomers are rapidly converted to ganciclovir by intestinal and hepatic esterases.

1.3 Previous Clinical Experience

The anti-EBV effect of valG has not been conclusively demonstrated or proven. On the other hand, data from infectious mononucleosis intervention trials document that two weeks of valA therapy resulted in a statistically significant reduction in oral EBV shedding, accompanied by a clinical benefit (1, 2), and valA is currently used for the therapy of severe cases of infectious mononucleosis in the community (1, 3).

Oral acyclovir has been shown to prevent CMV disease in post-KTx recipients (4-7) and valA in particular has been shown to reduce the incidence and delay the onset of CMV disease in both CMV seronegative patients ($P<0.001$) and CMV seropositive patients ($P=0.03$) (8). But since that trial did not include a comparison arm with the current standard of care which is valG and did not provide information on the anti-EBV effect of the valA, our study is critical in proving the effectiveness of valA for CMV and EBV prophylaxis.

ValG is associated with adverse events including diarrhea, fever, nausea, vomiting, tremor, leucopenia, neutropenia, anemia and thrombocytopenia in $\geq 20\%$ of patients based on their package insert which we have attached. ValG induced leucopenia often necessitates a reduction in immunosuppressive therapy, increasing the risk of allograft rejection. Fewer severe adverse events are related to valA, including rash (8%), abdominal pain (1% to 11%), nausea (5% to 15%), vomiting (less than 1% to 6%), headache (13% to 38%) and fatigue (8%). Very high doses of valA (8g/day) for post-KTx CMV prophylaxis was shown to have no severe or treatment-limiting side effects compared to placebo (8).

1.4 Dose Rationale and Risk/Benefits

Prior research at the University of Minnesota has shown that valacyclovir 1g every 8 hours for a total daily dose of 3g is well tolerated and was associated with a reduction in EBV excretion (1) in patients with infectious mononucleosis. Subsequently a study done at the University of Minnesota to characterize the pharmacokinetics and explore the pharmacodynamics of acyclovir in plasma and oral washings of 8 subjects with EBV infectious mononucleosis receiving the same daily dose of valacyclovir (3g) as a twice daily dosing of 1500 mg twice daily demonstrated safety and showed that the quantity of EBV DNA in oral washings and blood, and the severity of illness, measured by a graded scale, decreased during treatment (9).

Therefore in order to increase the likelihood of compliance in our patients, we have decided to utilize 1.5g twice a day dosing of valacyclovir and since it was shown to be effective as therapy in the above study, we hypothesize that it will be adequate for anti-viral prophylaxis as intended in this study. The dose will of course be adjusted based on GFR and in pediatric patients based on their weight as detailed in package insert and below.

No major side effects are anticipated since even very high doses of valA (8g/day), for post-KTx CMV prophylaxis were shown to have no severe or treatment-limiting side effects compared to placebo (10).

2 Study Objectives

Primary Objectives:

To compare the effectiveness of valacyclovir (valA) compared valganciclovir (valG) in the prevention of EBV and CMV viremia post-KTx.

To compare the proportion of patients requiring dose reduction or cessation of valA compared to valG due to adverse drug side effects.

Secondary Objective:

To identify the presence and quantity of EBV and CMV in renal tissue biopsies from kidney transplant recipients.

3 Study Design

This is a single-center, prospective, randomized, pilot study of up to 200 kidney transplant recipients from the University of Minnesota Medical Center. Randomization of subjects will be in a 1:1 ratio to receive either ValA or standard of care regimen of ValG. Duration of therapy will be 3-13 months.

Subjects will be assessed weekly then monthly for medication compliance, as well as assessing adverse events. Subjects will be assessed at their routine clinic visits, or via email/telephone. Subjects will be followed for a total of 12-13 months, or for an additional 30 days after stop of the drug for adverse events.

Blood samples will be collected by using left-over standard of care samples for immunosuppression drug analysis. From these samples, qualitative PCR assay (qPCR) will assess CMV and EBV for up to six months post study drug cessation. Complete blood count and metabolic panels will be collected clinically, and results recorded for this study. CMV and EBV IgG and IgM levels will be measured bi-annually until seroconversion. In the cases where blood is not drawn for clinical purposes at least once a month, 10-15ml of the subject's blood may be collected for this testing for research purposes. Surveillance kidney transplant biopsies are obtained at the time of transplant, 3 months post-transplant, 12 months post-transplant, and as clinically indicated. For the duration of subject study participation, kidney tissue (two to three cores) from any biopsy will be shared with the research team.

Subjects will be followed-up regularly by the research team during the first year post transplant. During these follow-up assessments, the research team will assess drug adherence as well as evaluate side effects. If subjects are seen during a standard of care visit, laboratory values and a review of medical records will also be performed to assess any potential adverse events.

4 Subject Selection and Withdrawal

4.1 *Inclusion Criteria*

- Adult or pediatric kidney transplant recipients
 - Adult cases are defined as patients transplanted and cared for at the University of Minnesota Medical Center, East Bank campus.
 - Pediatric cases are defined as patients transplanted and cared for at the University of Minnesota Masonic Children's Hospital.
- Consent to participate in the study.

4.2 *Exclusion Criteria*

- Documented allergy to valA or valG

- Recipients that are unable to independently understand the consent form.
- Pregnant

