6.6 Known Adverse Effects

As extracted from the package inserts for the study drugs, these are the known adverse effects for this protocol.

	Val G	Val A
COMMON Side Effects	headache nausea abdominal pain hematologic toxicity diarrhea fever tremor	headache nausea abdominal pain

	graft rejection vomiting hypertension upper respiratory infection urinary tract infection insomnia	
RARE adverse reactions	acute renal failure allergic reaction bleeding complications nervous system effects: agitation, hallucinations, confusion, delirium, seizures, swelling of the brain general pain, fatigue, weakness, edema abnormal lab results that might indicate abnormal organ function skin rash cough shortness of breath	acute renal failure allergic reaction bleeding complications nervous system effects: agitation, hallucinations, confusion, delirium, seizures, swelling of the brain

6.7 **Subject Compliance Monitoring**

Subjects will be asked to adhere to their prescribed treatment and dosage. Medication adherence will be assessed by the study team during routine visits, by reviewing the medical record, and by communication with the subject or guardian (table in section 5.4).

6.8 **Prior and Concomitant Therapy**

All prior and concomitant therapies will be documented and allowed as per standard of care procedures. Provided there are no direct interactions with the randomized medication, all medications will be prescribed as standard of care. Management of all viral disease is as per physician and will not be protocolled by research procedures.

6.9 **Blinding of Study Drug**

Not applicable.

7 Statistical Plan

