7.1 Primary Study Endpoints

The primary study endpoints are as follows:

1. Incidence and duration of CMV and EBV viremia and magnitude of viremia as measured by area under the viral load-time curve of recipients who become viremic with CMV and/or EBV in the first year post-Ktx.
2. Incidence of subjects developing drug related side effects requiring dose reduction or cessation.
3. Presence of EBV and or CMV in renal tissue (protocol biopsies).

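### The tolerability objective counts only antiviral dose changes, and no endpoint compares leucopenia, MMF reduction or rejection, so leucopenia on valG handled by cutting MMF alone scores as no event

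*Combined protocol and SAP*

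**What the plan says.** **Objective and endpoint.** Section 2 sets as a primary objective "To compare the proportion of patients requiring dose reduction or cessation of valA compared to valG due to adverse drug side effects". The matching item in 7.1 is "Incidence of subjects developing drug related side effects requiring dose reduction or cessation". The objective ties the dose change to the two antivirals; the endpoint leaves the drug unnamed.

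**Rationale.** Section 1 says "Combined therapy with MMF and valG frequently results in leucopenia associated infection or leucopenia necessitating reduction in MMF doses, increasing the risk of rejection". Section 1.3 says "ValG induced leucopenia often necessitates a reduction in immunosuppressive therapy, increasing the risk of allograft rejection". Section 1.1 expects valA, if its efficacy holds up, to bring fewer leucopenia-related infections and "a lower incidence of rejection by allowing the use of standard MMF doses".

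**Other endpoints.** The remaining primary endpoints in 7.1 are viremia and virus in renal tissue. Section 7.2 lists demographics, transplant characteristics and infection history. Section 7.3 is headed as safety endpoints but contains an interim rule on viremia.

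**Data collected.** Section 3 states "Complete blood count and metabolic panels will be collected clinically, and results recorded for this study". Section 6.8 states "All prior and concomitant therapies will be documented and allowed as per standard of care procedures".

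**The concern.** The harm attributed to valG runs through another drug: valG lowers the white count, MMF is cut in response, and rejection risk rises. The objective looks only at the antiviral. If the clinician cuts MMF and leaves valG unchanged, the patient has suffered the harm described in the rationale and is scored as tolerating valG.

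Two things are at stake. First, the trial could finish without any planned comparison of the outcomes on which its tolerability case rests. Second, the tolerability comparison may look more alike between arms than it really is, because whether an event is counted depends on which drug the clinician reduces. Treatment is open label (6.9) and concomitant therapy follows standard of care (6.8), so that choice is made with knowledge of the arm.

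**Working it through.** The documents give no rate, effect size, power or test for this endpoint, so there is no planned figure to reproduce. The check has two parts.

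**1. The text, outcome by outcome**

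| Link in the rationale (1, 1.1, 1.3) | Recorded? | Compared between arms in 7.1–7.3? |
|---|---|---|
| Leucopenia | Yes: CBC results (3, 5.4); adverse events (8, 8.1) | No |
| MMF or immunosuppression reduction | Concomitant therapy documented (6.8) | No under the section 2 objective; unclear under 7.1 item 2 |
| Leucopenia-associated infection | As an adverse event (8.1) | No |
| Rejection | Medical record review (3) | No |
| Antiviral reduction or cessation | Yes | Yes (2; 7.1 item 2) |

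Serious adverse event reporting does not fill the gap. Section 8 excludes known effects of the study drug and of transplantation, with rejection on the list, unless life-threatening or fatal.

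**2. An illustration of what masking could cost**

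Inputs:
- 100 per arm: 200 subjects randomized 1:1 (sections 3 and 7.4).
- Two-sided Fisher exact test at 0.05. The study summary names this test for viremia incidence; applying it here is an assumption.
- True rate of side effects leading to some dose action: 20% on valG. This is an assumption. It borrows the floor of the figure in 1.3 for a list that includes "leucopenia, neutropenia, anemia and thrombocytopenia in" at least 20% of patients, but also covers diarrhea, nausea, fever and tremor. It is not a rate of toxicity needing dose action.
- The same rate on valA: 5% (assumed).
- Masked share f, meaning events handled by cutting MMF only: not given, so varied.

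Formulas:
- Visible valG rate = 0.20 × (1 − f).
- Visible valA rate = 0.05 × (1 − f) if masking is equal in both arms, or 0.05 if masking occurs on valG only.
- Power = sum, over all pairs of event counts (i, j) whose Fisher p-value is ≤ 0.05, of Bin(i; 100, visible valG rate) × Bin(j; 100, visible valA rate).

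| f | Equal masking: rates | Power | valG-only masking: rates | Power |
|---|---|---|---|---|
| 0 | 20% v 5% | 88% | 20% v 5% | 88% |
| 50% | 10% v 2.5% | 50% | 10% v 5% | 19% |
| 75% | 5% v 1.25% | 16% | 5% v 5% | no difference left |

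With masking on valG only and f = 25%, the rates are 15% v 5% and power is 59%.

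Under equal masking the risk ratio stays at 4 (20/5 = 10/2.5 = 5/1.25), while the risk difference falls from 15 to 7.5 to 3.75 percentage points. Under valG-only masking the ratio itself falls, from 4 (20/5) to 2 (10/5) to 1 (5/5).

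**The case against.** **The endpoint wording could be read more broadly.** Item 2 of 7.1 names no drug and could be taken to include an MMF cut for valG leucopenia. This stands. Part of the defect is a mismatch between objective and endpoint, and it would be wrong to say that both count only antiviral changes. But the objective in section 2 points the other way, and coding cannot be left to interpretation.

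**A reader might infer that MMF-only management is the usual course.** The documents do not say so. They say leucopenia frequently or often leads to an MMF or immunosuppression cut; they do not say valG then continues unchanged. A patient whose valG is also reduced or stopped is counted. Only MMF-only cases are missed, and their share is unknown.

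**A reader might infer that the endpoint is biased against valA by a known amount.** That is not supported either. Under equal masking the risk ratio is untouched; the loss is in events, power and risk difference. The relative comparison is pulled towards no difference only if masking falls more heavily on valG. The rationale makes that plausible, but nothing quantifies it.

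**A reader might infer that the whole trial rests on this harm.** It does not. Prevention of viremia and cost are also stated reasons, the MMF and rejection benefit in 1.1 is conditional on efficacy, and this is a pilot. What remains is that tolerability is a primary objective and this chain is its main argument.

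**The data are partly there.** Section 8 makes a laboratory abnormality that needs active management, a dose change included, an adverse event. True, but recording is not a planned comparison.

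**Folding MMF cuts into the primary endpoint would cause trouble of its own.** Section 1 says EBV viremia is managed by reducing immunosuppression, so a composite could mix efficacy failure into tolerability, and attribution in an open-label trial is partly subjective. This stands and shapes the fix: antiviral dose change is a legitimate endpoint and should be kept.

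**Conclusion.** The gap is real. Under the section 2 objective, a valG patient with leucopenia managed by an MMF cut alone is event-free, 7.1 leaves the matter open, and no listed endpoint compares leucopenia, MMF reduction or rejection. As written, the trial can report how often each antiviral was reduced or stopped. It has no planned analysis of whether valA spares MMF or avoids the consequences.

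This conclusion rests on the text alone. The size does not: 88% power falling to about 50% or about 19% with half the events masked depends on assumed rates, an assumed test and an assumed share, and shows only that the loss could be material. The point should be addressed, but it does not invalidate the existing endpoint.

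**What to change.** 1. Keep the antiviral dose-change endpoint. Align section 2 and 7.1 item 2 so that both name the drug whose reduction or cessation counts.
2. Add to 7.2, as separate between-arm secondary endpoints:
   - (a) leucopenia or neutropenia at a prespecified CBC threshold;
   - (b) reduction or interruption of MMF or other immunosuppression attributed to leucopenia or another suspected antiviral side effect, with the reason recorded and cuts made for viremia coded separately;
   - (c) treated rejection.
3. Reconcile 5.3, which describes monthly safety labs for valA recipients only, with the schedule in 5.4, which shows CBC and BMP without limiting them to one arm. Endpoint (a) is interpretable only if CBC ascertainment is equal.

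The cost is endpoint wording and one CRF field for the reason for an immunosuppression change. The sources are the CBCs, concomitant therapy records and chart review already planned. The downside is some subjectivity in attribution because the trial is open label; reporting (a), which needs no attribution, beside (b) limits it.

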4.3.2 Data Collection and Follow-up for Withdrawn Subjects

Subjects will be followed for 12-18 months post-transplant procedure. Please refer to Table 1 for data points and frequency.

5 Study Procedures

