5.3 Laboratory Testing

Blood is collected in accordance to standard of care procedures for these patients. Left-over blood from the clinical laboratories of subjects will be obtained and tested for CMV and EBV quantitative PCR assay (qPCR), at minimum weekly for the first month and monthly for the first year to year and a half post-KTx. Acyclovir levels will be measured

at 1 month in patients randomized to valA. CMV and EBV IgG and IgM levels will be measured bi-annually for patients who are seronegative until seroconversion after which they will no longer be checked. Safety labs include complete blood counts and basic metabolic panels which will be done for recipients randomized to valA monthly while participating in the study.

If the labs are not being collected at a minimum of weekly for the first month and then monthly for the first year, the study team will collect 10-15mL of blood from the subjects for research procedures.

Half to one core of kidney tissue will be obtained, if available, from all kidney transplant biopsies performed during the first year post-KTx.

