5.4 Schedule of Events

All assessments will be completed during routine clinical visits when feasible. If the participant does not have a scheduled clinic visit, the participant or parent/guardian can choose to receive an email or phone call follow-up of drug adherence and adverse events. Assessments will continue until at least 30 days after last dose of anti-viral.

Visit Schedule	Pre-KTx	KTx	Weekly During Month 1	Monthly through End of Study Period
CBC and BMP ¹ (routine clinical lab)	X		X	X
CMV PCR, EBV PCR ² ([name] research lab)	X		X	X
CMV IgG, EBV IgG & IgM ² ([name] research lab)	X			X ³
Acyclovir levels				X ⁴
Kidney bx tissue ⁵		X		X ³
Medication compliance			X	X ⁶
Adverse Events assessment			X	X ⁶

1 CBCs and BMP are performed routinely in post-transplant patients. If these are not done clinically, we will collect and perform for research safety monitoring

2 PCRs will be run using leftover blood collected clinically. If no leftover blood is available, we will collect a research specimen.

- 3 Month 6 only
- 4. Month 1 only if randomized to valA
- 5. Kidney biopsies are performed routinely during the first year post-transplant. Paraffin-embedded scrolls will be requested from leftover tissue.
- 6. Completed monthly until 1 month after cessation of the treatment

6 Study Drug

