6.3 Duration of Therapy

Duration of therapy is dependent on donor and recipient antibody status.

Adult subjects will be treated with their assigned study drug (ValA or ValG) for **three months**, unless the donor is antibody positive and the recipient is antibody negative (D+R-) to CMV/EBV, then patient will get six months of prophylaxis.

Pediatric transplant recipients will be treated for **twelve months except** if both the donor and the recipient are antibody negative (**D- R-**) for both CMV and EBV, subjects will be treated for **three months**.

Patients that are randomized to ValA that develop CMV disease or CMV viremia X2 may discontinue ValA and begin standard of care treatment with ValG. At that time they will continue research related follow up but ValA use is up to the discretion of the treating physician. At that time all protocol directed safety follow up will be discontinued; however, outcomes will be followed until month 12.

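### The protocol gives two PCR windows for primary endpoint 1; the section 3 rule, if followed, would stop testing before month 12 in some patients

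*Combined protocol and SAP*

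**What the plan says.** Four parts of the protocol bear on how long viremia is looked for.

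- **Section 3 (Study Design)** ties PCR to drug stop: "qualitative PCR assay (qPCR) will assess CMV and EBV for up to six months post study drug cessation". It calls the assay qualitative. The same section puts total follow-up at 12-13 months.
- **Section 5.3 (Laboratory Testing)** ties PCR to transplant: "at minimum weekly for the first month and monthly for the first year to year and a half post-KTx". It calls the assay quantitative. It adds research blood draws by the study team as a back-up: "If the labs are not being collected at a minimum of weekly for the first month and then monthly for the first year".
- **Section 5.4 (Schedule of Events)** marks CMV and EBV PCR under "Monthly through End of Study Period". That end point is not defined.
- **Section 4.3.2**, on withdrawn subjects, states: "Subjects will be followed for 12-18 months post-transplant procedure".

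Primary endpoint 1 (section 7.1) is the incidence, duration and viral-load area of viremia in "recipients who become viremic with CMV and/or EBV in the first year post-Ktx". Primary endpoint 2 is side effects that lead to dose reduction or cessation.

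Drug duration is set in section 6.3. Adults are treated "for three months, unless the donor is antibody positive and the recipient is antibody negative", in which case they get six months. Children get twelve months, or three if donor and recipient are both negative for both viruses.

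**The concern.** The endpoint has a fixed window of one year from transplant. Section 3 gives a testing window that moves with the date of drug stop. For the two to agree, six months after drug stop must reach month 12 in everyone, and with three-month courses it does not.

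Two things are at stake. The first is completeness: part of the endpoint year would go untested in patients on the standard adult course. The second is comparability. Drug can stop early because of side effects, which is an event after randomisation, is counted in primary endpoint 2, and is one on which sections 1.1 and 1.3 expect valacyclovir to do better. A testing window that depends on that event could differ in length between the arms. The planned analyses in the Study Summary are a Fisher exact test on incidence and a Mann-Whitney test on viral-load area. Neither allows for unequal observation time, and the plan does not say how untested months are handled.

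The assay label matters too. Area under the viral load-time curve cannot be computed from qualitative results.

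**Working it through.** **Inputs.** Drug duration d in months (section 6.3); PCR for at most 6 months after drug stop (section 3); endpoint window of 12 months (section 7.1). I assume that drug starts at about the time of transplant. Section 5.1 allows consent up to 7 days after surgery for deceased-donor recipients, and a start that late would move the ends below by about a week.

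**Formulas under section 3 alone.**

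Latest PCR month = d + 6. Untested endpoint months = max(0, 12 − (d + 6)) = max(0, 6 − d).

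Planned courses:

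| Group | d | Latest PCR month | Untested months | Share of year |
|---|---|---|---|---|
| Adult, not donor-positive/recipient-negative | 3 | 3 + 6 = 9 | 3 | 3/12 = 25% |
| Adult, donor-positive/recipient-negative | 6 | 6 + 6 = 12 | 0 | 0% |
| Child, both negative for both viruses | 3 | 3 + 6 = 9 | 3 | 25% |
| Other children | 12 | 12 + 6 = 18 | 0 | 0% |

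Early stops (the stop months are illustrations; the protocol gives no rates):

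| Stop month | Latest PCR month | Untested months | Share of year |
|---|---|---|---|
| 1 | 7 | 5 | 5/12 = 42% |
| 2 | 8 | 4 | 4/12 = 33% |
| 4 | 10 | 2 | 2/12 = 17% |
| 5 | 11 | 1 | 1/12 = 8% |

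Any stop before month 6 leaves a gap. Because section 3 sets an upper limit, these are the smallest gaps that its wording allows.

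**How much of the gap could differ by arm.** Planned duration depends on age group and serostatus, not on treatment, so 1:1 randomisation should balance that part. Only the extra months lost through stopping early can differ. For a stop at month 1, the extra loss is 5 − 3 = 2 months in a patient planned for three months, and 5 − 0 = 5 months in one planned for six or twelve. A dose reduction without cessation changes nothing.

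**Under sections 5.3 and 5.4.** Monthly PCR from transplant to at least month 12 gives a gap of 0 in every group.

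**Consistency with the other follow-up statements.** For planned courses, section 3 gives last PCR months of 9 to 18. Sections 4.3.2 and 5.3 give 12 to 18. Section 3's own total follow-up of 12-13 months fits neither range in full.

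**The case against.** The strongest reply is that one summary sentence is being set against the detailed sections, and that those agree with one another. Section 5.3 sets a minimum frequency and provides back-up draws for the whole first year. In the 5.4 schedule, the compliance and adverse-event rows carry a footnote ending them one month after treatment stops; the PCR row carries no such footnote, and a research specimen is taken when no leftover blood exists. Section 4.3.2 keeps withdrawn subjects for 12-18 months. Section 6.3 follows outcomes to month 12 in valacyclovir patients who stop for CMV disease or repeated viremia. The section 3 phrase may also have been written with the longer courses in mind: 6 + 6 = 12 and 12 + 6 = 18 match the 12-18 months given elsewhere.

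Most of this stands. A reader might infer from section 3 that the trial will stop testing standard adults at month 9; the documents taken together do not support that. The reply still does not settle the matter. No clause says which section prevails. The end of the study period in 5.4 is undefined. The month-12 commitment in 6.3 covers only one arm and one reason for stopping, so it leaves out valganciclovir patients and anyone who stops for side effects. Section 3 says that research blood may be collected, where 5.3 says that it will be. And the longer-course reading does not fit three-month patients, who include the standard adult group.

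Two further inferences go too far. One is that viremia after prophylaxis would be missed: even under section 3, up to six months of testing after drug stop remain, and the documents do not say how much viremia arises later than that. The other is that the arm with more early stopping would look better. Shorter observation lowers the detected incidence, but stopping also removes prophylaxis, which may raise the true incidence.

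**Conclusion.** The contradiction is real and bears on primary endpoint 1. Section 3 states a rule that, if followed, leaves 3 of 12 endpoint months untested in three-month adults and in children negative for both viruses, and leaves some gap in anyone who stops before month 6. Under 5.3 and 5.4 the gap is zero. Most of the text favours the second reading, so this is an inconsistency in the protocol and not evidence that surveillance will fall short.

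If section 3 were applied, the planned-duration part of the gap would shorten observation about equally in both arms. The early-stopping part could differ by arm. Its size depends on cessation rates that the documents do not give, and its direction is not determined. A claim of bias for or against either drug would go beyond the documents.

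The conclusion rests on the calendar arithmetic, on drug starting at about the time of transplant, and on the absence of any statement of precedence between sections.

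**What to change.** 1. In section 3, replace the PCR phrase with: *quantitative PCR weekly in month 1 and at least monthly to month 12 post-transplant in every randomised subject who has not withdrawn consent, regardless of when or why study drug stops.* The consent exception is needed because section 4.3 ends all follow-up when consent is withdrawn. This wording also removes the qualitative/quantitative mismatch.
2. In section 5.4, define the end of the study period for the PCR row so that it is no earlier than month 12, in line with 5.3.
3. In section 7, make month 12 the common cut-off for incidence, duration and area under the curve. Samples taken later, to month 18, may be reported separately.

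The cost is wording only. Section 5.3 already plans the monthly tests and the back-up draws through the first year, and no dose or treatment rule changes.
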